7.3 Study Drugs

7.3.1 Exposure

The following information on drug exposure will be presented for each treatment group for the SAF, FAS and PPS:

Duration of exposure in treatment period will be summarized in two ways.

- Descriptive statistics will be presented by treatment group.
- Exposure time will be categorized according to the following categories by treatment group:
 - less than 14 days
 - at least 14 days, less than 28 days
 - at least 28 days, less than 56 days
 - at least 56 days, less than 84 days
 - 84 days or more
 - Unknown.

Counts and percentages of subjects in each of these categories will be summarized for each treatment group for the SAF, FAS and PPS.

7.3.2 Treatment Compliance

Overall compliance of the study drug (Mirabegron/Placebo) and Tamsulosin with the dosing schedule will be examined for subjects whose total study drug and Tamsulosin count and first and last days of treatment are known for the SAF, FAS and PPS.

Percent overall compliance of the study drug and Tamsulosin during treatment period will be summarized in two ways for the SAF, FAS and PPS:

- Descriptive statistics will be presented by treatment group.
- Percent compliance will be categorized according to the following categories by treatment group:
 - less than 50%
 - at least 50%, less or equal to 80%
 - greater than 80%
 - Unknown.

7.4 Analysis of Efficacy

Continuous variables will be summarized using descriptive statistics, including mean, standard deviation, minimum, Q1, median, Q3 and maximum. Categorical variables will be described using absolute and relative frequency.

7.4.1 Analysis of Primary Endpoint(s)

7.4.1.1 Primary Analysis of Primary Endpoint

The primary efficacy endpoint, change from Baseline to End of Treatment in the mean number of micturitions per 24 hours, will be analyzed using an Analysis of Covariance

(ANCOVA), including treatment group and region as fixed factors and baseline as a covariate for the FAS. Within the framework of the ANCOVA model, point estimates and two-sided 95% confidence intervals (95% CI) for the mean change from Baseline both within and between treatment groups (point estimate will be calculated as [Mirabegron + Tamsulosin] minus [PLACEBO + Tamsulosin]) will be calculated. The two-sided significance level will be set at 5%.

The SAS code used to implement ANCOVA will be similar to that shown below:

```
PROC GLM;  
  CLASS treatment region;  
  MODEL chg = treatment region base / SS3;  
  LSMEANS treatment / ALPHA=0.05 CL PDIFF=CONTROL("PLACEBO + Tamsulosin");  
RUN;
```

Here, variables in the MODEL statement are:

- chg: Change from baseline to End of Treatment in the mean number of micturitions per 24 hours
- treatment: Treatment group (PLACEBO + Tamsulosin/Mirabegron + Tamsulosin)
- region: Region (Japan/Korea)
- base: Baseline mean number of micturitions per 24 hours

The hypotheses for the treatment group comparisons are as follows:

H₀: The change from Baseline to End of Treatment in the mean number of micturitions over 24 hours is the same in subjects who received mirabegron compared to those who received placebo.

H₁: The change from Baseline to End of Treatment in the mean number of micturitions over 24 hours is not the same in subjects who received mirabegron compared to those who received placebo.

The End of Treatment assessment will be analyzed.

Separately, ANCOVA including the interaction between treatment and other covariates will be investigated in order to present information of significance of interactions.

The SAS code used to implement ANCOVA including the interaction will be similar to that shown below:

```
PROC GLM;  
  CLASS treatment region;  
  MODEL chg = treatment region base treatment*region treatment*base / SS3;  
RUN;
```

Here, variables in the MODEL statement are same as those for ANCOVA not including the interaction.

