The study will be conducted in Japan (~50 centers) and Korea (~5 centers). The target enrollment is 550 subjects, with 275 randomized to each treatment group.

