7.4.1 Analysis of Primary Endpoint

7.4.1.1 Primary Analysis

The primary efficacy endpoint, change from Baseline to End of Treatment in the mean number of micturitions per 24 hours, will be analyzed using an Analysis of Covariance (ANCOVA), including treatment group and region as fixed factors and baseline as a covariate. Within the framework of the ANCOVA model, point estimates and two-sided 95% confidence intervals for the mean change from Baseline both within and between treatment groups will be calculated. The two-sided significance level will be set at 5%.

The hypotheses for the treatment group comparisons are as follows:

H_0 : The change from Baseline to End of Treatment in the mean number of micturitions over 24 hours is the same in subjects who received mirabegron compared to those who received placebo.

H_1 : The change from Baseline to End of Treatment in the mean number of micturitions over 24 hours is not the same in subjects who received mirabegron compared to those who received placebo.

The primary and secondary efficacy analyses will be conducted using the FAS, which includes all subjects who receive at least 1 dose of double-blind study medication *and* have both a Baseline and post-Baseline micturition assessment.

For those subjects who discontinue the study prematurely, the End-of-Treatment assessment will be analyzed. The End-of-Treatment assessment is defined as the last post-Baseline assessment during the double-blind study period for which primary efficacy data are available.

Continuous variables will be summarized using descriptive statistics, including mean, standard deviation, minimum, Q1, median, Q3 and maximum. Categorical variables will be described using absolute and relative frequency.

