3.3 Randomization

Subjects will be randomized 1:1 to receive mirabegron 50 mg or matching placebo once daily during the 12-week treatment period. The randomization will be stratified by site.

Randomization will be performed via Interactive Response Technology (IRT). Prior to the initiation of the study treatment, the site staff will contact the IRT in order to determine the randomly assigned treatment for each subject.

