7.4.1.4 Secondary Analysis of Primary Endpoint

The primary efficacy endpoint will also be analyzed using a Mixed Model Repeated Measure (MMRM). MMRM analysis will be conducted for change from baseline in the mean number of micturition episodes per 24 hours to post-baseline visits using the baseline the mean number of micturition episodes per 24 hours as a covariates, analysis visits and region as a fixed effect, subject as random effect and including interaction of [treatment group x visit] for FAS and PPS. For MMRM, Restricted Maximum Likelihood (REML) approach will be used, KENWARD-ROGER approximation will be used to estimate of degree of freedom of denominator, and ‘Unstructured’ will be assumed as structure of variance-covariance matrix. Though, when the calculation will not be converged, other covariance structures will be selected in the following order: ‘Unstructured Correlations’, ‘Heterogeneous Toeplitz’, ‘Heterogeneous First-Order Autoregressive’, ‘Toeplitz’, ‘First-Order Autoregressive’, ‘Compound Symmetry’, and ‘Variance Components’ instead. Within the framework of MMRM, point estimates and two-sided 95% CIs for the mean change from Baseline both within and between treatment groups (point estimate will be calculated as [Mirabegron + Tamsulosin] minus [PLACEBO + Tamsulosin]) will be calculated.

The SAS code used to implement MMRM will be similar to that shown below:

```
PROC MIXED method=REML;  
  CLASS treatment region visit usubjid;  
  MODEL chg = treatment region base visit treatment*visit / ddfm=KENWARDROGER;  
  REPEATED visit / type=UN subject=usubjid r;  
  LSMEANS treatment*visit / CL PDIFF=CONTROL("PLACEBO + Tamsulosin");  
RUN;
```

Here, variables in the MODEL statement are:

- chg: Change from baseline to End of Treatment in the mean number of micturitions per 24 hours
- treatment: Treatment group (PLACEBO + Tamsulosin/Mirabegron + Tamsulosin)
- region: Region (Japan/Korea)
- base: Baseline mean number of micturitions per 24 hours
- visit: Post-baseline visit (Week 4, Week 8, Week 12)
- usubjid: Subject Identifier

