7.4.2 Analysis of Secondary Endpoints

The secondary endpoints are actual value and the change from Baseline to post-baseline and End of Treatment in:

- Mean number of micturations/24 hours (except for End of Treatment visit)
- Mean number of urgency episodes/24 hours
- Mean number of urgency incontinence episodes/24 hours
- Mean number of incontinence episodes/24 hours
- Mean number of nocturia episodes
- Mean volume voided per micturition
- Total OABSS score
- Subscale scores (daytime frequency, nighttime frequency, urgency and urgency incontinence) from OABSS score
- Total IPSS score
- Subscale scores (storage subscale, voiding subscale and quality of life item) and individual scores from IPSS score
- Symptom Bother and total Health-Related QoL scores, as assessed by the OAB-q questionnaire.

For the changes in mean number of incontinence and urge incontinence episodes, the analysis will be based on those subjects who have at least 1 incontinence episode at Baseline.

For the change in the mean number of nocturia episodes, the analysis will be based on those subjects who had at least 1 nocturia episode at Baseline.

Concerning actual value and the change from baseline to post-baseline of the secondary endpoints, descriptive statistics will be calculated by treatment group at each visit and at the End of Treatment for FAS and PPS.

Mean (+/- SD) plot for actual value and change from baseline to post-baseline will be presented by treatment group for FAS. In addition, for mean number of micturations/24 hours, this plot will be presented by subgroups defined in section 7.4.4 for FAS.

Radar charts of the mean of actual value for OABSS and IPSS will be made to present relationship between each question by treatment group for FAS.

For individual score from OABSS score and IPSS score, frequency tabulations of scores will be presented for each treatment group at each visit and at the End of Treatment for FAS and PPS.

Except for the changes in mean number of micturations, incontinence and urge incontinence episodes, change from Baseline to End of Treatment of these endpoints will be analyzed using an ANCOVA (refer to section 7.4.1.1 for detail) for FAS and PPS.

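### Randomisation is stratified by site, but the primary ANCOVA, secondary ANCOVAs and MMRM adjust only for region; separately, the coded within-group means weight Japan and Korea equally

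*SAP*

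**What the plan says.** SAP 3.3 states: "The randomization will be stratified by site". Protocol 4.5 says the same. Protocol 2.2.1 plans about 50 centres in Japan and about 5 in Korea, and the synopsis plans 490 Japanese and 60 Korean subjects. Neither document gives a block size.

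The primary model in Protocol 7.4.1.1 is an ANCOVA "including treatment group and region as fixed factors and baseline as a covariate". SAP 7.4.1.1 repeats it, "including treatment group and region as fixed factors and baseline as a covariate for the FAS", and region there has two levels, Japan and Korea. The other secondary endpoints, apart from micturitions and the two incontinence counts, use the same model: SAP 7.4.2 says they "will be analyzed using an ANCOVA (refer to section 7.4.1.1 for detail) for FAS and PPS". The MMRM in SAP 7.4.1.4 is coded as "MODEL chg = treatment region base visit treatment*visit / ddfm=KENWARDROGER", again without site. The one sensitivity analysis of the primary endpoint (SAP 7.4.1.2) is the same model on the PPS.

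SAP 7.4.1.1 promises point estimates and 95% confidence intervals for the mean change within each group as well as between groups. The code is "LSMEANS treatment / ALPHA=0.05 CL PDIFF=CONTROL", with the placebo arm as control and no OM option. The LSMEANS statements for the subgroup analysis and the MMRM have no OM option either.

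**The concern.** There are two separate points.

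**(a) Site.** Stratifying by site largely balances site effects between the arms, so they add little to the true sampling variance of the treatment difference. A model without site still counts that variance as residual error. Region removes only the between-country part. If sites differ within country after baseline adjustment, the model standard error exceeds the true one, the confidence interval is too wide and the test is conservative. If sites do not differ, nothing is lost. What is at stake is a little efficiency and agreement between analysis and design.

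**(b) Country weights.** Without OM, SAS averages LS means over the levels of a class factor with equal weights. Each within-group mean then describes a half-Korean population, although about one subject in nine is to be Korean. The standard error is correct for that target, but the target is not the trial population. Neither model has a treatment-by-region term, so the treatment difference does not depend on these weights.

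**Working it through.** **Inputs from the documents.** Difference 0.7, SD 2.4, two-sided alpha 0.05, 248 per group in the FAS, 90% evaluable (SAP 4); 490 Japanese and 60 Korean subjects (protocol synopsis); about 55 sites.

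**Assumptions.** The site ICC after baseline adjustment (0, 0.02, 0.05, 0.10) and the block size (4 or 10) are not in the documents.

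**The plan's own figure.** n = 2 × (1.960 + 1.282)² × 2.4² / 0.7² = 247.1, so 248 per group. The SE of the difference is 2.4 × √(2/248) = 0.2155. Power is Φ(0.7/0.2155 − 1.960) = 90.1%. The stated 248 and 90% are reproduced.

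**(a) Approximation.** With arms balanced within site, true SE / model SE ≈ √(1 − ICC). The actual alpha without site is 2 × [1 − Φ(1.960/√(1 − ICC))].

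| ICC | Model SE too large by | Actual alpha | Power, site omitted | Power, site included (df cost ignored) |
|---|---|---|---|---|
| 0 | 0% | 0.050 | 90.1% | 90.1% |
| 0.02 | 1.0% | 0.048 | 90.3% | 90.7% |
| 0.05 | 2.6% | 0.044 | 90.7% | 91.5% |
| 0.10 | 5.4% | 0.039 | 91.3% | 92.8% |

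**(a) Simulation.** 55 sites of unequal size (50 Japan, 5 Korea), permuted blocks within site, 550 randomised, 10% random loss (495 analysed), total SD 2.4, difference 0.7, 25,000 runs. The random-site model used REML with df of n − 55 − 1, or n − 3 when the site variance was estimated as zero, in place of Kenward-Roger. Blocks of 4:

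| ICC | Mean SE: region only / random site | Power: region only / random site | Type I error: region only / random site |
|---|---|---|---|
| 0 | 0.2157 / 0.2150 | 90.1% / 90.2% | 4.8% / 4.9% |
| 0.02 | 0.2156 / 0.2136 | 90.1% / 90.5% | 4.6% / 4.9% |
| 0.05 | 0.2155 / 0.2109 | 90.1% / 90.8% | 4.8% / 5.3% |
| 0.10 | 0.2152 / 0.2056 | 91.2% / 92.7% | 4.1% / 4.9% |

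The region-only SE is 2.2% larger at ICC 0.05 (0.2155/0.2109) and 4.7% larger at ICC 0.10 (0.2152/0.2056). At ICC 0.10 the region-only model SE of 0.2152 compares with an empirical SE of 0.2053.

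With blocks of 10, the power gains at the four ICCs are 0.1, 0.3, 0.6 and 1.4 points. The paired Monte Carlo SE of a gain is at most 0.08 points. Type I error is 5.1, 4.9, 4.5 and 4.3% without site, and 5.1, 5.1, 4.9 and 5.2% with the random intercept.

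Unpooled fixed site effects are a poor alternative. With about 495/55 = 9 analysed subjects per site, they cost 0.8 points at ICC 0 with blocks of 4 (90.1% to 89.3%) and 1.3 points with blocks of 10 (89.9% to 88.6%).

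**(b) Within-group means.** The planned Korean share is 60/550 = 0.109, but the coded weight is 0.50. In the additive model:

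- Equal weights: variance = 5.76/248 + (0.5 − 0.109)² × 5.76 × (1/441.9 + 1/54.1) = 0.0232 + 0.0183 = 0.0415, so the SE is 0.204.
- Observed margins: 2.4/√248 = 0.152.
- Ratio: 0.204/0.152 = 1.34. The 95% half-width is 0.40 against 0.30.
- Weight per subject, Korea against Japan: (0.5/60)/(0.5/490) = 490/60 = 8.2.
- Shift of each mean: (0.5 − 0.109) = 0.39 times any Korea–Japan difference in mean change. That difference is not in the documents; assumed values of 0.5 and 1.0 give shifts of 0.20 and 0.39.
- The SE of the treatment difference is 0.2155 under either weighting.

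**The case against.** The strongest objection is one of proportion. Protocol and SAP fix the same primary model before unblinding, its estimate is unbiased, and its error is on the conservative side. The upper end of the power gain needs an ICC of 0.10, which nothing in the documents supports; at 0.02 or less the gain is at most 0.4 points. On that view, a sentence of justification or a site-adjusted sensitivity analysis would do. The small size stands and sets the weight of this point. It does not remove the mismatch with the design, because no planned analysis includes site.

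Kenward-Roger itself was not simulated, and one setting showed a type I error of 5.3% for the random-site model. This is a fair caution. The other settings lay between 4.9% and 5.2%, and a 6,000-run repeat of that setting gave 4.8%, so there is no consistent excess.

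There are also loose ends. The rank ANCOVA for the incontinence endpoints stratifies by region only. The subgroup analyses rerun the primary model in sets as small as Korea, with about 60 × 0.9 = 54 analysed subjects at about 5 sites. The SAP would have to say whether the site term carries over.

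On the country weights, the SAP calls its code similar to what will be run, and descriptive means and region-specific ANCOVAs are planned too. The weighted mean would therefore not be the only group result. But nothing says that observed margins will be used or that equal weighting is intended.

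**Conclusion.** Both points hold.

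(a) Leaving site out makes the primary inference slightly conservative if sites differ within country. Over assumed ICCs of 0 to 0.10, a random site intercept gains 0.1 to 1.5 power points, and the planned SE is up to 4.7% larger than the random-site SE with blocks of 4. There is no bias, no added false-positive risk and no shortfall against 90% power. The size rests on an ICC and a block size that the documents do not give.

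(b) As coded, the adjusted within-group means give Korea 50% weight against a planned 11%, and their SE is 34% larger than with observed margins. This follows from the planned numbers, the planning SD and the SAS default. It leaves the treatment difference, its interval and the primary p-value unchanged.

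The changes should be made, but neither point threatens the primary conclusion.

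**What to change.** (a) Before unblinding, add site within region as a random intercept to the primary and secondary ANCOVAs. Keep treatment, region and baseline as fixed effects, and use Kenward-Roger degrees of freedom. Do not use unpooled fixed site effects. If the site variance is estimated as zero, the model reduces to the planned one. State whether the site term applies in the subgroup analyses. In the MMRM a site term is optional, because that model already needs a fallback list for when "when the calculation will not be converged, other covariance structures will be selected in the following order".

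The cost is a move from PROC GLM to a mixed model, recorded in the protocol synopsis and Protocol 7.4.1.1 as well as the SAP. The protocol fixes the model, and Protocol 8.3.3 requires changes to be documented.

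(b) Add the OM option to the LSMEANS statements, or state that the within-group means weight the two countries equally. This costs one option or one sentence.

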7.4.1.2 Sensitivity Analysis of Primary Endpoint

An analysis of the primary endpoint will be conducted on the PPS. The method used for this analysis will be identical to the primary analysis described in section [7.4.1.1](#).

7.4.1.3 Subgroup Analysis of Primary Endpoint

The analyses described in section 7.4.1.1 will be conducted by subgroups defined in section 7.8. The SAS code used to implement ANCOVA by subgroups will be similar to that shown below:

```
PROC GLM;  
  BY grouping variables;  
  CLASS treatment region;  
  MODEL chg = treatment region base / SS3;  
  LSMEANS treatment / ALPHA=0.05 CL PDIFF=CONTROL("PLACEBO + Tamsulosin");  
RUN;
```

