7.4.1.3 Subgroup Analysis

Subgroup analyses will include analyses by geographic region and by urgency incontinence at Baseline. Further details on subgroup analyses will be provided in the SAP.

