4 SAMPLE SIZE

The sample size for this study was based on 248 subjects per treatment group (using the Full Analysis Set [FAS]) to provide 90% power to detect a 0.7 reduction in the mean number of micturitions/24 hours in the mirabegron group compared to the placebo group, at a two-sided alpha level of 0.05. A standard deviation (SD) of 2.4 is assumed.

Assumptions for the mean reduction and SD are based on data from previous studies. If 90% of the randomized subjects are evaluable for efficacy, 550 subjects should be randomized, with 275 subjects randomized to each treatment group.

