7 STATISTICAL METHODOLOGY

7.1 General Considerations

Assessment at Visit 2 (Day 1) will be treated as baseline for efficacy and safety analysis.

The End of Treatment assessment is defined as the last post-Baseline assessment during the double-blind study period for which the primary efficacy data are available.

For continuous variables, descriptive statistics will include the number of subjects (n), mean, standard deviation, minimum, Q1 (25th percentile), median, Q3 (75th percentile) and maximum. Frequencies and percentages will be displayed for categorical data. Percentages by categories will be based on the number of subjects with no missing data, i.e. will add up to 100%.

Summaries based on FAS and PPS (e.g. disposition, baseline and efficacy data) will be presented by planned treatment group, unless specifically stated otherwise. Safety analysis and other summaries based on SAF will be presented by actual treatment received.

All statistical comparisons will be made using two sided tests at the $\alpha=0.05$ significance level unless specifically stated otherwise. All null hypotheses will be of no treatment difference, all alternative hypotheses will be two-sided, unless specifically stated otherwise.

All data processing, summarization, and analyses will be performed using Windows SAS[®] Version 9.4. Specifications for table, figures, and data listing formats can be found in the Tables, Listings and Figures (TLF) specifications for this study.

For the definition of subgroups of interest please refer to section [7.8](#)

Total and subscale score of OABSS, IPSS and OAB-q are as follows:

Name of score	Subscale score	Calculation	Range
IPSS (Question 1-7 and Quality Life Item)	Storage Subscale	Sum of Question 2,4 and 7	0-15
	Voiding Subscale-1	Sum of Question 3, 5 and 6	0-15
	Voiding Subscale-2	Sum of Question 1, 3, 5 and 6	0-20
	Quality of Life Item	-	0-6
	Total Index Score	Sum of Question 1 to 7	0-35
OABSS (Question 1-4)	Daytime frequency	Question 1	0-2
	Nighttime frequency	Question 2	0-3
	Urgency	Question 3	0-5
	Urgency incontinence	Question 4	0-5
	Total Score	Sum of Question 1 to 4	0-15
OAB-q (Question 1-33)	Symptom bother	Sum of Q1-8	0-100
	Coping	Sum of Q9,11,16,21,22,26,32,33	0-100
	Concern	Sum of Q12,13,14,19,23,25,29	0-100
	Sleep	Sum of Q10,15,17,24,30	0-100
	Social Interaction	Sum of Q18,20,27,28,31	0-100
	Total Health-Related Quality of Life scores	Sum of OAB-q subscale scores (Coping, Concern, Sleep, Social Interaction)t	0-100

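### Except for region, the subgroup analyses of the primary endpoint include no treatment-by-subgroup term, so the planned output does not directly estimate or test whether the effect differs

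*SAP*

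**What the plan says.** Protocol section 7.4.1.3 states: "Subgroup analyses will include analyses by geographic region and by urgency incontinence at Baseline". It leaves further detail to the SAP.

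SAP section 7.4.1.3 supplies that detail: "The analyses described in section 7.4.1.1 will be conducted by subgroups defined in section 7.8". The code is PROC GLM with a BY statement on the grouping variable. The model contains treatment, region and baseline, and the LSMEANS statement asks for confidence limits and the difference from control. Each stratum therefore yields a treatment difference, a 95% confidence interval and a p-value. Section 7.1 adds "All statistical comparisons will be made using two sided tests at the" 0.05 level unless stated otherwise.

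Section 7.8 lists eight grouping variables: Region, Age1, Age2 (three levels), BMI, duration of the primary diagnosis, urgency incontinence at baseline, PVR (split at the median) and Qmax. For the Region subgroups, a footnote removes region from the model.

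The only model that crosses treatment with a covariate is the additional one in section 7.4.1.1: "MODEL chg = treatment region base treatment*region treatment*base". Its stated purpose is to report whether interactions are significant. Section 7.4.4 adds descriptive statistics by subgroup. Neither document gives a rule for interpreting the subgroup results.

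**The concern.** Whether the effect differs between two strata is a question about the difference between two treatment effects. For seven of the eight grouping variables, no planned analysis estimates or tests that difference. Age1 and Age2 are two cuts of one factor, so six distinct characteristics are affected.

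The output will allow stratum p-values to be set side by side. Reading a significant stratum next to a non-significant one as evidence of a differential effect is a known error, because each stratum has far less power than the whole trial. At stake is a false statement that the drug works in one kind of patient and not in another, most visibly for urgency incontinence at baseline. Running the section 7.4.1.1 interaction model within each stratum would not help, since a stratum contains only one level of the subgroup variable.

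**Working it through.** **Inputs.** SAP section 4: "248 subjects per treatment group (using the Full Analysis Set [FAS]) to provide 90% power to detect a 0.7 reduction", and "at a two-sided alpha level of 0.05. A standard deviation (SD) of 2.4 is assumed". SAP section 3.3: "Subjects will be randomized 1:1 to receive mirabegron 50 mg or matching placebo". SAP section 7.8 splits PVR at the median, giving about 248/2 = 124 per arm in each half. This is the only split whose size the documents fix at about one half. The two-sample calculation takes 2.4 as the residual SD, as the sample-size section does.

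**Plan's own figure.** n per arm = 2 × (1.960 + 1.282)² × 2.4² / 0.7² = 247.03, rounded up to 248. The noncentral-t power at 248 per arm is 90.0%. The figure reproduces.

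**One half of a 50:50 split, true effect 0.7 in both halves.**
- SE = 2.4 × √(2/124) = 0.305, and 0.7/0.305 = 2.30.
- Power is 62.8% by noncentral t (63.2% by the normal approximation).
- The halves share no subjects, so P(exactly one significant) = 2 × 0.628 × 0.372 = 0.467 (46.5% by the normal approximation; 46.6% in 200,000 simulated trials).

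**Other effect sizes, 50:50 split.**

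| True effect | Source | SD | Power per half | Exactly one significant |
|---|---|---|---|---|
| 0.56 | Table 5: 2.04 − 1.48 | 2.4 | 44.8% | 49% |
| 0.70 | SAP section 4 | 2.4 | 62.8% | 47% |
| 0.81 | Table 4: 1.67 − 0.86 | 2.4 | 75.4% | 37% |
| 0.81 | Table 4, with its own SDs | 2.354 and 2.212 | 79.4% | 33% |

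**Unequal splits, effect 0.7, SD 2.4.** The documents do not give these stratum sizes, so the splits are assumptions. P(exactly one significant) = p₁(1 − p₂) + p₂(1 − p₁).
- 40:60: powers 53.4% and 70.8%, result 48.6%.
- 30:70: powers 42.4% and 77.3%, result 54.2%.
- 20:80: powers 30.1% and 82.6%, result 63.0%.

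**With an interaction test.** When both strata truly have the same effect, the test declares a difference in 5% of trials per variable (4.98% in simulation).

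**Precision of that test, equal split.**
- Main-effect SE = 2.4 × √(2/248) = 0.2155, so the interaction SE is 2 × 0.2155 = 0.431.
- Power for an interaction of 0.7: Φ(0.7/0.431 − 1.96) = Φ(−0.336) = 37%.
- 90% power needs an interaction of (1.96 + 1.282) × 0.431 = 1.40, twice the planned treatment effect.

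**The case against.** Several stronger readings are tempting, and the documents do not support them.

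- **A reader might infer that heterogeneity can be judged only by comparing p-values.** It cannot be put that strongly. Each stratum also yields an estimate and a 95% confidence interval. The strata are disjoint, so anyone can take the difference of the two estimates with standard error √(SE₁² + SE₂²). The pre-specified contrast is missing, not the means of forming one.
- **A reader might infer that equal effects will often look different.** The 47% concerns verdicts at the 5% level. With equal effects and equal strata, the two 95% intervals fail to overlap only when |Z| exceeds 2 × 1.96/√2 = 2.77, which is about 0.6% of trials. The risk falls on a reader who compares significance and ignores the intervals.
- **A reader might infer that the sponsor plans to claim differential benefit from stratum p-values.** No such rule appears. Section 7.8 speaks of summarizing, and hypotheses are stated only for the overall comparison. Table layouts are left to a separate specification, so it is not known whether subgroup p-values will be displayed.
- **A reader might infer that the trial's main conclusion is at risk.** The primary test, its type I error and the sample size are untouched.

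It can also be said that an interaction test with 37% power adds little. That is a reason to report the interaction with its interval and to read a null result cautiously. It is not a reason to leave the stratum results without a direct comparison.

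**Conclusion.** The point holds as a modest improvement to the subgroup analysis. Seven of the eight grouping variables, covering six distinct characteristics, have no treatment-by-subgroup term, although section 7.4.1.1 already seeks this information for region and baseline count. If stratum verdicts are compared, truly equal effects give a mixed verdict in about 47% of trials for the PVR median split at the planned effect, against 5% for an interaction test. This rests on an effect of 0.7 in both halves, a residual SD of 2.4 and 124 per arm in each half. Across the effects in protocol Tables 4 and 5 the rate is about 33% to 49%; the lower end uses Table 4's own SDs and is 37% at SD 2.4. Figures for other splits, including urgency incontinence at baseline, depend on assumed stratum sizes and rise as the split becomes less equal.

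**What to change.** For each non-region variable in SAP section 7.8, add one ANCOVA on the FAS with treatment, subgroup, treatment-by-subgroup, region and baseline. Keep the existing treatment-by-region model for Region, where a separate subgroup term would duplicate region.

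Report the stratum estimates with 95% confidence intervals, together with the interaction estimate, its interval and its p-value. Label all of these exploratory. State that any claim of a differential effect rests on the interaction and not on stratum p-values, and that a non-significant interaction does not show homogeneity.

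The cost is one extra model per variable, with no new data and no change to the primary analysis. The pooled model assumes a common baseline slope, region effect and residual variance across strata, which the separate models do not. With several variables tested at 5%, some false positives are expected: about 26% for at least one, if there were six independent 50:50 factors. The exploratory label should therefore stay.
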